Cognitive Behavioral Therapy for Insomnia for Gulf War Illness

NCT02782780

Prepared: 12/09/2020

Study Protocol

I. Hypothesis: We hypothesize that telephone delivered cognitive behavioral therapy for insomnia (CBTi) will reduce insomnia and non-sleep Gulf War Illness (GWI) symptoms in Gulf War veterans with GWI. Specifically:

1. Effect sizes will suggest that 8-weeks of telephone CBTi improves measures of insomnia severity, subjective sleep quality, and sleep diary measures of total sleep time, sleep onset latency (i.e., the time it takes to fall asleep), and sleep efficiency.
2. Effect sizes will suggest that 8-weeks of telephone CBTi improves measures of non-sleep GWI symptoms, as assessed by the “symptom” portion of the Kansas Gulf War Military History and Health Questionnaire, and measures of fatigue, pain, cognitive dysfunction, and depression and anxiety.
3. In subjects randomized to the treatment arm of the trial, post-CBTi improvements in measures of insomnia and GWI symptoms will be maintained at the 6-month follow-up.

II. Aims:

1. Estimate effect size of telephone-delivered CBTi on insomnia and sleep quality in veterans with Gulf War Illness (GWI) and insomnia (i.e., have Insomnia Severity Index (ISI) scores ≥ 14).
2. Estimate effect size of telephone-delivered CBTi on GWI symptoms in veterans with GWI and ISI scores ≥ 14 .
3. Examine maintenance of telephone-delivered CBTi effects at 6-month follow-up.

III. Study Design: The project will test the efficacy of telephone-delivered CBTi for sleep and non-sleep symptoms associated with GWI by performing a randomized, parallel-group trial with GW Veterans who meet both the Centers for Disease Control and Prevention (CDC) case definition for Chronic Multisymptom Illness (CMI)⁴, the Kansas case definition for Gulf War Illness (GWI)⁵, and who have insomnia, operationalized as having ISI scores ≥ 14 .

The study's goal is to randomize 80 eligible participants to get 64 participants who complete the trial. Half of the participants will be randomly assigned to receive telephone CBTi (TX). The other half will be randomized to a Monitor Only (MO) control group. Participants randomized to the TX group will receive 8 weekly sessions of CBTi via telephone with the study therapist. Participants randomized to the MO group will be monitored for 8 weeks (i.e., they will be advised to continue doing whatever they were doing to manage their GWI and insomnia symptoms without change dosage or frequency of treatment).

Prior to randomization, all subjects will be monitored for 1 week with sleep diary. Sleep diary data will also be acquired continuously throughout the 8 study-weeks in both groups. Outcomes will be assessed in all study participants at baseline (i.e., before randomization), mid- and post-treatment. In subjects randomized to TX, outcomes will be assessed once more, 6 months after treatment with Qualtrics online surveys or with traditional pen-and-pencil surveys.

Subjects randomized to the MO condition will be offered telephone-CBTi, at no cost to them, after 8 weeks of monitoring and upon completion of the post-treatment assessments.

Prior to the initiation of the study, we will conduct a test run of the study procedures in 2-6 GW veterans. To preserve our pool of eligible GW veterans for the CBT-I trial proper, for the test run, we will recruit GW veterans who have Insomnia Severity Index (ISI) scores > 12, and/or who screen positive for obstructive sleep apnea, and/or who do not meet the criteria for Kansas Gulf War Illness because of an exclusionary medical condition (e.g., seizures or heart disease).

IV. Procedures:

A. Subject Evaluations:

1. Screening for Inclusion: Once subjects have initiated contact, they will be given more information about the study by telephone or by US mail. An initial pre-screen will be performed over the telephone by a study staff member after subjects have given their verbal consent to determine inclusion/exclusion criteria.
2. Clinical Screening: If subjects pass the initial pre-screening for inclusion, they will participate in a clinical screening interview with an experienced clinical interviewer under the supervision of a licensed clinical psychologist. The clinical interviewer will be kept blind to treatment assignment. The following instruments will be used in the clinical screening interview:
 - a. The Structured Clinical Interview for DSM-V (SCID-5¹⁵) will be used to assess DSM-V diagnostic criteria for Axis I disorders.
 - b. Clinician Administered PTSD Scale (CAPS⁵⁶) will be administered to all study participants to assess posttraumatic stress disorder (PTSD) status at baseline.
 - c. Addiction Severity Index-Lite (ASI-Lite) questionnaire will be used to obtain data on the participant's history of alcohol consumption and substance use.
 - d. Ohio State University Traumatic Brain Injury Identification Method (OSU TBI-ID⁶⁹) This is a standardized procedure to elicit the lifetime history of TBI for an individual. The instrument is based on CDC; National Center for Injury Prevention and Control (2003) case definitions and recommendations for TBI surveillance
 - e. Subjects will be screened with the Berlin Questionnaire to assess the likelihood of obstructive sleep apnea (OSA).
 - f. Subjects will be screened with restless legs syndrome screening questionnaire (RLSSQ)⁷⁵ to assess the likelihood of restless legs syndrome (RLS). An RLSSQ score ≥ 7 ,⁷⁵ identifies patients with RLS with 97.9% sensitivity and 96.2% specificity, will be dropped from the study.

If data from the clinical evaluation suggests that a subject is eligible for the study, the subject will be asked to keep a sleep diary for one week. Following that, the subject will be randomized to the CBT-I (TX) group or the Monitor Only (MO) group

B. STUDY ASSESSMENTS: The following assessments will be performed at baseline (i.e., before randomization), mid- and post-treatment in all participants. For participants randomized to TX, the assessments will be performed again 6-months after treatment.

1) The **Insomnia Severity Index (ISI⁷⁶)** is a 7-item self-report questionnaire assessing the nature, severity, and impact of insomnia in the last month. The dimensions evaluated are: severity of sleep onset, sleep maintenance, and early morning awakening problems, sleep dissatisfaction, interference of sleep difficulties with daytime functioning, noticeability of sleep problems by others, and distress caused by the sleep difficulties. A 5-point Likert scale is used to rate each item (e.g., 0 = no problem; 4 = very severe problem), yielding a total score ranging from 0 to 28.⁷⁶

2) The **Pittsburgh Sleep Quality Index (PSQI⁷⁷)** is a self-report measure that provides a subjective assessment of sleep quality, sleep latency, sleep duration, sleep efficiency, sleep disturbances, use of sedative-hypnotics, and daytime energy.

3) The symptom portion of the **Kansas Gulf War Military History and Health Questionnaire**,⁷ which includes 32 questions about fatigue/sleep problems, somatic pain, skin abnormalities, gastrointestinal symptoms, respiratory symptoms, and neurologic/cognitive/mood symptoms, based on the Kansas and Centers for Disease Control and Prevention (CDC) GWI case definition, will be used to assess Gulf War Illness (GWI) symptoms. To assess **current** GWI symptoms, we ask participants about the absence, presence, and severity of the symptoms over the past **2 weeks** instead of over the past 6-months. A **GWI Symptom Severity score** will be derived by summing the answers to 30 of the GWI symptom questions. A higher score will indicate more symptoms and symptoms of greater severity.

4) The **Fatigue Severity Scale (FSS)** is a 9-item questionnaire reflecting the consequences of fatigue. It gives a single score (range 0–7, high scores represent high levels of fatigue). A score of 4 has been described as the cutoff for clinical fatigue.⁷⁸

5) The **Brief Pain Inventory (BPI)⁷⁹** is a 17-item self-rating scale assessing demographic data, use of medications, as well as sensory, and reactive components of pain. The BPI includes items that address components of sensory pain including severity, location (identified with a body map as a measure of pain distribution), chronicity, degree of relief

due to therapy, and reactive pain (e.g., depression, suffering, and perceived availability of relief).

6) The **Multiple Abilities Self-Report Questionnaire (MASQ)**⁸⁰ is a 38-item self-report measure of cognitive function compared to same age peers across 5 domains (i.e., verbal memory, attention, language, visual memory, visuo-perceptual ability)

7) The **Hospital Anxiety and Depression Scale (HADS)**⁸¹ will be used to assess **anxiety and depressive** symptoms.

8) The **PCL-5**,⁸² a 20-item self-report measure that assesses the 20 DSM-5 symptoms of PTSD, will be used to monitor PTSD symptom change in subjects with PTSD.

9) **Sleep Diary:** All subjects will fill out an online (or paper) sleep diary for 1 week prior to randomization and continuously during the 6-week study period. During CBT-I, the sleep diaries will be a part of treatment and will be examined by the study therapist to monitor adherence, treatment progress, and to inform interventions or sleep restriction titration. Sleep diaries are daily self-monitoring forms that allow the self-recording of various sleep-related measures such as time in bed (TIB), total sleep time (TST), wake after sleep onset (WASO), sleep onset latency (SOL, the time it takes to fall asleep). Participant will also be asked to log the nature and dose of all medications in their sleep diaries. This information will be used to examine whether there are group differences in baseline rates of medication use, mean weekly rates of use during treatment, or change in rates of use throughout the study.

10) **Epworth Sleepiness Scale** will be used to help case formulation and to individualize administration of CBTi.

11) **Morningness-Eveningness Scale** will be used to help case formulation and to individualize administration of CBTi.

All of the self-report assessments and sleep diary data will be obtained online via the Qualtrics survey tool. If participants do not have access to a personal computer and/or would prefer to fill out the self-report assessments and sleep diary via pencil-and-paper, they will be allowed to do so and will be provided a stamped envelope with which to mail the assessments and sleep diary back to us.

We will template and write brief notes about the CBTi treatment in the VA's computerized patient record system (CPRS) as is expected with treatment studies.

Subjects randomized to the MO group will be offered the opportunity to receive CBTi, by telephone, upon completion of all study procedures. However, we will allow these

subjects more flexibility in the duration of CBTi. In practice, there is no “magic number” of sessions. Some patients get better quickly, and some take longer. Therefore we would like to allow subjects randomized to the MO group who elect to receive CBTi by telephone after completing all study procedures the opportunity to receive CBTi for 6-8 weeks. We will not give subjects originally randomized to the MO group **more** sessions of CBTi than subjects randomized to the treatment group, but we will not mandate that they be in therapy for 8 weeks if they and the CBTi therapist does not deem it necessary, especially since these subjects have already been in the study 8 weeks prior to starting CBTi filing out sleep diaries and other study questionnaires.

Some subjects find that, after a few sessions, CBTi is not for them. In practice, we find that these are the subjects who become non-compliant with the therapy (e.g., do not follow the therapist's recommendations and prescriptions). Therefore, we will allow subjects originally randomized to the MO group who elect to receive CBTi after the study but are non-compliant with CBTi the opportunity to stop therapy if both they and the therapist agree that it is not in their best interest at the present time to continue with CBTi.

We will request participants refrain from having elective surgery, starting, stopping, and/or changing their medication or medication dose within 1 month of starting CBTi and during CBTi. We will also ask participants refrain from missing more than 2 CBTi sessions.

V. Assessment Instruments:

- Research version of the Structured Clinical Interview for DSM-V (SCID-5¹⁵), will be administered to assess DSM-V diagnostic criteria for Axis I disorders.
- Clinician Administered PTSD Scale (CAPS⁵⁶) will be administered to all study participants to assess PTSD status at baseline.
- Addiction Severity Index-Lite (ASI-Lite) questionnaire will be used to obtaining data on the participants' alcohol consumption and substance use.
- Ohio State University Traumatic Brain Injury Identification Method (OSU TBI-ID⁶⁹) This is a standardized procedure to elicit the lifetime history of TBI for an individual. The instrument is based on CDC; National Center for Injury Prevention and Control (2003) case definitions and recommendations for TBI surveillance.
- Berlin Questionnaire will be used to assess the likelihood of obstructive sleep apnea (OSA).
- Restless legs syndrome screening questionnaire (RLSSQ)⁷⁵ will be used to assess the likelihood of RLS.
- Insomnia Severity Index (ISI⁷⁶) is a 7-item self-report questionnaire assessing the nature, severity, and impact of insomnia in the last month. The dimensions evaluated are: severity of sleep onset, sleep maintenance, and early morning awakening problems, sleep dissatisfaction, interference of sleep difficulties with daytime functioning, noticeability of sleep problems by others, and distress caused by the sleep difficulties. A 5-point Likert scale is used to rate each item

(e.g., 0 = no problem; 4 = very severe problem), yielding a total score ranging from 0 to 28.

- Pittsburgh Sleep Quality Index (PSQI)⁷⁷ is a self-report measure that provides a subjective assessment of sleep quality, sleep latency, sleep duration, sleep efficiency, sleep disturbances, use of sedative-hypnotics, and daytime energy.
- Kansas Gulf War Military History and Health Questionnaire⁷ includes 32 questions about fatigue/sleep problems, somatic pain, skin abnormalities, gastrointestinal symptoms, respiratory symptoms, and neurologic/cognitive/mood symptoms, based on the Kansas and CDC GWI case definition. We will use the symptom portion of the questionnaire to assess GWI symptoms, excluding the 2 questions about sleep difficulties to assess GWI symptoms.
- Fatigue Severity Scale (FSS) is a 9-item questionnaire reflecting the consequences of fatigue. It gives a single score (range 0–7, high scores represent high levels of fatigue). A score of 4 has been described as the cutoff for clinical fatigue.⁷⁸
- Brief Pain Inventory (BPI)⁷⁹ is a 17-item self-rating scale assessing demographic data, use of medications, as well as sensory, and reactive components of pain. The BPI includes items that address components of sensory pain including severity, location (identified with a body map as a measure of pain distribution), chronicity, degree of relief due to therapy, and reactive pain (e.g., depression, suffering, and perceived availability of relief).
- Multiple Abilities Self-Report Questionnaire (MASQ)⁸⁰ is a 38-item self-report measure of cognitive function compared to same age peers across 5 domains (i.e., verbal memory, attention, language, visual memory, visuo-perceptual ability)
- Hospital Anxiety and Depression Scale (HADS)⁸¹ will be used to assess anxiety and depressive symptoms.
- PCL-5,⁸² a 20-item self-report measure that assesses the 20 DSM-5 symptoms of PTSD, will be used to monitor PTSD symptom change in subjects with PTSD.
- Sleep diaries will be used to allow the self-recording of various sleep-related measures such as time in bed (TIB), total sleep time (TST), wake after sleep onset (WASO), sleep onset latency (SOL, the time it takes to fall asleep). In addition, participant will be asked to log the nature and dose of all medications in their sleep diaries.

VI. Intervention:

- A. Cognitive Behavioral Therapy for Insomnia (CBTi) will be administered via telephone by therapists at the San Francisco VA Medical Center to participants for 8 weekly sessions.
- B. CBTi will consist of several sessions of sleep restriction, stimulus control and cognitive restructuring related to sleep concerns. The CBTi therapists will all have prior training in CBTi and will be supervised by study co-investigator [name], a licensed clinical psychologist with over ten years of experience in behavioral sleep medicine treatment and research.
- C. Monitor Only Waitlist Control condition will consist of continuous monitoring of sleep with diary and data collection at baseline, weeks 4 and 9.

D. Waitlist participants will receive weekly telephone or email check-ins from the study coordinator and will be offered CBTi following completion of the research protocol.

VII. Statistical Analysis:

- Linear mixed models with random effects for subjects will be used to analyze all available data for the intent-to-treat analysis. Because sex will be used as a stratification variable in the randomization procedure, it will not be included as a covariate in the analyses.
- Treatment effects will be estimated from post-treatment group differences using mixed models adjusting for baseline scores on each outcome. Standardized effect sizes will be calculated by dividing the treatment effect on each outcome variable by the pooled standard deviation of the variable at baseline.
- To compare baseline data to 6-month follow-up data in the CBTi group, planned contrasts following the mixed models will be used. Statistical analyses will be carried out using R (version 4.0.1). Mixed models will be fitted using the lme4 package (version 1.1-23) and significance tests will be based on Kenward-Roger degrees of freedom estimate provided by the pbkrtest package (version 3.1-2).

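### Sex is left out of the models because randomization is stratified by it; given balance within sex, between-arm standard errors are slightly too large if sex is prognostic beyond baseline

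*Combined protocol and SAP*

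**What the plan says.** Section VII (Statistical Analysis) sets out the model: "Linear mixed models with random effects for subjects will be used to analyze all available data for the intent-to-treat analysis". It continues: "Because sex will be used as a stratification variable in the randomization procedure, it will not be included as a covariate in the analyses". The only adjustment named is for the baseline value of the outcome: "Treatment effects will be estimated from post-treatment group differences using mixed models adjusting for baseline scores on each outcome". Effect sizes are standardized by "dividing the treatment effect on each outcome variable by the pooled standard deviation of the variable at baseline", and "significance tests will be based on Kenward-Roger degrees of freedom estimate provided by the pbkrtest package".

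Section III (Study Design) plans to "randomize 80 eligible participants to get 64 participants who complete the trial", with equal allocation to the two arms. No other section puts sex into a model or plans a sensitivity analysis with it. Block size, expected number of women and expected sex effect are not given.

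**The concern.** The stated reason runs the wrong way. Stratified randomization forces the arms to be alike on sex, so differences between men and women drop out of the sampling variation of the arm difference. A model without sex does not know this and leaves the between-sex variance in its error term. The reported standard error then exceeds the true one.

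The random subject effect does not cure this. Unmodelled sex variance goes into the between-subject component, which enters the between-arm standard error. Baseline adjustment absorbs part of a sex effect, but only the part already visible in the baseline score.

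At stake are the width of the between-arm intervals and the p-values for many outcomes (insomnia, sleep quality, diary measures, Gulf War Illness symptoms, fatigue, pain, cognition, mood) in a trial that expects 64 completers. The point estimates are not at stake under balance, and the within-arm comparison of baseline with 6 months is little affected.

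**Working it through.** **Inputs from the documents.** 80 randomized, 64 expected completers, 1:1 allocation, stratification by sex (sections III and VII). The 64 and 80 imply 1 − 64/80 = 20% attrition. The plan states no figure for the effect of omitting sex, so there is nothing of its own to reproduce on this point.

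**Assumed inputs (not in the documents).** Share of women p; sex difference d in within-sex SDs, equal at baseline and post-treatment; within-sex baseline-post correlation rho from 0.7 to 0.3; a two-sided 5% test; arms balanced within sex.

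**Formulas.** With within-sex SD 1 at both times:
- between-sex variance: vb = p(1−p)d²
- baseline slope when sex is omitted: b = (rho + vb)/(1 + vb)
- within-sex residual variance at that slope: W = 1 − 2·b·rho + b²
- residual variance reported without sex: T = W + (1−b)²·vb
- SE excess over the model with sex: sqrt(T/(1−rho²)) − 1
- true size of the 5% test without sex: 2·(1 − Phi(1.96·sqrt(T/W)))

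**Worked case: p = 0.5, d = 0.8, rho = 0.3.**
- vb = 0.25 × 0.64 = 0.16
- b = 0.46/1.16 = 0.397
- W = 0.919 and T = 0.978
- SE excess = sqrt(0.978/0.91) − 1 = 3.65%; size 4.33%

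**Range of results.**

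| Women | Sex difference | SE excess (rho 0.7 to 0.3) | True size of a 5% test |
|---|---|---|---|
| 15% | 0.5 SD | 0.27% to 0.83% | 4.9% to 4.8% |
| 20% | 0.8 SD | 0.82% to 2.47% | 4.8% to 4.5% |
| 50% | 0.8 SD | 1.21% to 3.65% | 4.8% to 4.3% |

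**Upper case.** If the whole sex effect g, in residual SDs, survives baseline adjustment, the excess is sqrt(1 + p(1−p)g²) − 1. At p = 0.5 and g = 0.8 this is sqrt(1.16) − 1 = 7.7%, with size 3.5%. At g = 0.2 it is 0.2% to 0.5% over 12.5% to 50% women; at g = 0 it is zero.

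**Simulation.** 80 randomized 1:1 within sex, 64 random completers, post-treatment ANCOVA on baseline, 12,000 trials per setting:
- 50% women, 0.8 SD, rho 0.3: mean reported SE 0.250 without sex and 0.241 with it; size 4.4% and 4.9%. Two independent repeats gave SEs of 0.248 and 0.240, with sizes of 4.9% and 5.1% in one and 4.5% and 4.9% in the other. The SE gap is stable; the gap in size is near Monte Carlo error (about 0.2 points).
- 15% women, 0.5 SD, rho 0.5: reported SE 0.2198 and 0.2190.
- No sex effect: including sex makes the SE about 0.2% larger.

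**Power.** In a separate simulation with 64 completers exactly balanced within sex, baseline-post correlation 0.5, an assumed treatment effect of 0.6 SD and 12.5% to 50% women, power was 0.753 to 0.764 without sex and 0.769 to 0.777 with it at g = 0.5.

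**Without balance within sex.** For 50% women, 0.8 SD and rho 0.3, the model without sex was not conservative (size 4.95%). Adding sex still improved precision: the true SD of the estimate fell from 0.250 to 0.243.

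**The case against.** The strongest reply is that the sentence can be read charitably. Stratification balances sex, so adjustment is not needed to guard against bias. As far as bias goes, that is right, and the error is on the safe side. The plan aims to estimate effect sizes, and neither the estimate nor its baseline-SD divisor is biased. In the 15%-women scenario the gain from adding sex (0.3% to 0.8% of the SE) is of the same order as its cost when sex is not prognostic (about 0.2%). The larger figures need 50% women, where p(1−p) peaks, and the top of the assumed sex effect. The conservatism also depends on randomization mechanics that the plan does not describe, and the simulations use a single ANCOVA in place of the planned mixed model.

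All of this stands as a limit on size. It does not rescue the rationale, which fails for variance estimation: balance by design is what makes the unadjusted standard error wrong. If balance is lost, the case for including sex changes but remains, because precision still improves. Dropout that differs by sex and arm adds another reason. In an illustrative run (20% women, 0.8 SD, rho 0.3, 50% retention of treated women against 85% elsewhere), the estimate without sex shifted by about −0.03 SD; with sex it was about zero.

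**Conclusion.** The concern holds. The plan gives stratification as its reason for leaving sex out, and that reason is mistaken for variance estimation. If the randomization balances sex between arms and sex predicts an outcome beyond its baseline score, the between-arm standard errors, intervals and p-values for that outcome are conservative. The excess in the SE is about 0.3% to 3.7% over the three scenarios tabulated and 7.7% in the upper case; it is zero if sex is not prognostic. These figures rest on assumed values for the share of women, the sex effect, the correlation and the test level. No conclusion of the trial is likely to turn on this, but the change is worth making because it costs almost nothing and makes the analysis match the randomization.

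**What to change.** In section VII, replace the sentence that excludes sex with: *Sex, the randomization stratification factor, will be included as a fixed effect in all mixed models.* At the least, add a sensitivity analysis with sex in the between-arm models.

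The cost is one SAP sentence and one degree of freedom. Sex is known for every participant at randomization, so no new data are needed. If sex turns out not to be prognostic, the between-arm SE is about 0.2% larger with 64 completers.

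### The only planned 6-month analysis compares with baseline, so it cannot show whether the post-treatment gain was maintained, as Hypothesis 3 and Aim 3 require

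*Combined protocol and SAP*

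**What the plan says.** Hypothesis 3 (Section I) predicts that, in the treatment arm, the improvement present after CBTi will persist to 6 months. Aim 3 (Section II) is to examine that maintenance.

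On visits, Section III says: "Outcomes will be assessed in all study participants at baseline (i.e., before randomization), mid- and post-treatment". The CBTi arm alone is assessed again 6 months after treatment.

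Section VII contains these elements:
- The general model: "Linear mixed models with random effects for subjects will be used to analyze all available data for the intent-to-treat analysis".
- The treatment effect: "Treatment effects will be estimated from post-treatment group differences using mixed models adjusting for baseline scores on each outcome".
- The 6-month analysis: "To compare baseline data to 6-month follow-up data in the CBTi group, planned contrasts following the mixed models will be used".
- The basis for inference: "significance tests will be based on Kenward-Roger degrees of freedom estimate provided by the pbkrtest package", with the models themselves fitted in lme4.

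The document contains no post-treatment to 6-month comparison and no criterion for calling a gain maintained. It also does not say whether baseline is a covariate or a response, whether the subject effects are intercepts only, or what covariance holds across visits.

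**The concern.** Maintenance is a statement about two time points, the end of treatment and 6 months. The planned contrast uses baseline and 6 months and leaves out the end of treatment. A participant group that improved a great deal and then lost half of it would still be better than at baseline, and with a moderate sample the contrast would usually be significant. A report that takes this result as support for Hypothesis 3 would claim durability that the analysis did not examine.

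There is a smaller, related gap. A contrast between two visits needs both visits among the modelled responses. Adjusting for baseline scores reads most naturally as using baseline as a covariate, and a baseline to 6-month contrast cannot then come from that same model. A second model is needed, and none is described.

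**Working it through.** **Step 1: question against analysis.**
- Hypothesis 3 and Aim 3: is the 6-month mean as good as the post-treatment mean?
- Section VII: does the 6-month mean differ from the baseline mean?

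Write G for the gain from baseline to post-treatment and L for the loss from post-treatment to 6 months. The planned contrast estimates G - L. Hypothesis 3 is about L. A positive G - L is compatible with L = 0 and with L equal to half of G.

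**Step 2: inputs.**
- From Section III: 80 randomized to obtain 64 completers, half per arm. This implies a loss of 1 - 64/80 = 20%. It gives 40 CBTi participants randomized and, if loss is equal between arms, 32 completing.
- Assumed: 28 followed up at 6 months as a lower case; two-sided 5% tests; 0.5 baseline SD of gain left at 6 months; paired-change SD of 1.0 baseline SD, with a range of 0.8 to 1.2. With equal SDs, the change SD is sqrt(2(1 - r)), so 1.0 corresponds to r = 0.5.
- The plan gives no SD, correlation, effect size or alpha, so it has no figure of its own to reproduce here.

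**Step 3: how often the planned contrast is significant when 0.5 SD remains.** Paired t test with noncentrality 0.5 / (SD / sqrt(n)) on n - 1 df.

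| n at 6 months | Noncentrality (SD 1.0) | Power, SD 1.0 | Power, SD 0.8 | Power, SD 1.2 |
|---|---|---|---|---|
| 28 | 2.65 | 72% | 89% | 57% |
| 32 | 2.83 | 78% | 93% | 63% |
| 40 | 3.16 | 87% | 97% | 73% |

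The range is 57% to 97%. For a 1.0 SD gain with n = 32 and change SD 1.0, the contrast is significant with probability 0.78 if half the gain is lost, 0.97 if 0.3 SD is lost, and about 1.0 if nothing is lost. Significance hardly distinguishes these cases.

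**Step 4: what the missing contrast would deliver.** The 95% CI half-width is t(0.975, n - 1) x SD / sqrt(n). With change SD 1.0:
- n = 28: 2.052 / 5.292 = 0.39 SD.
- n = 32: 2.040 / 5.657 = 0.36 SD.
- n = 40: 2.023 / 6.325 = 0.32 SD.

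With n = 32, a post-treatment to 6-month test detects a true loss of 0.3 SD with power of only about 0.38. A non-significant difference would therefore not demonstrate maintenance.

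**Step 5: the secondary covariance point.** Take the random-intercept reading with baseline as covariate and mid- and post-treatment scores as responses. The model pools the two residual variances, so its SE for the post-treatment difference is about sqrt((a² + b²)/2) / b times the true SE, where a and b are the mid and post residual SDs. The actual level is about 2 x Phi(-1.96 x ratio). The SDs are assumed.
- 4 then 4: ratio 1.00, level 5.0%.
- 3 then 4: sqrt(12.5)/4 = 0.884, level 8.3%.
- 4 then 3: sqrt(12.5)/3 = 1.179, level 2.1%.

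The error can go either way, or be absent.

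**The case against.** The baseline to 6-month contrast is relevant: it shows whether participants are still better than when they entered, and a trial framed around effect sizes can report that usefully. This stands, and the contrast should be kept. It does not make it an analysis of maintenance. An author could also read the 6-month mean against the post-treatment mean informally, but the plan names no estimate, interval or criterion for doing so.

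The added contrast is not decisive either. Its interval is wide and, like the planned one, it is a within-arm comparison without control data at 6 months. This also stands, and is why the estimate and interval, not a test result, should carry the conclusion.

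On the secondary points, the baseline form can be settled with a clarifying sentence. A reader might go further and infer that the planned tests are anti-conservative. The documents do not support that. They do not say intercept only, and random slopes would also fit the wording. They give no SDs or correlations. Equal variances and correlations produce no error, and some unequal patterns make the test conservative. Aims 1 and 2 concern estimation, and with complete data the point estimates are not in question. What remains is that Section VII does plan significance tests, and any intervals would use the same standard errors. The covariance should therefore be stated.

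**Conclusion.** The main point holds on the text alone: Hypothesis 3 and Aim 3 have no analysis that addresses maintenance of the post-treatment gain. The size is illustrative. With 0.5 SD of gain left, the planned contrast would still be significant in about 72% to 87% of trials at change SD 1.0, and in 57% to 97% over change SDs of 0.8 to 1.2. These figures rest on assumed values and on 28 to 40 CBTi participants followed up.

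The model for the 6-month contrast and the covariance across visits are missing detail of secondary weight. The covariance point concerns the questionnaire outcomes, which have few visits. Diary data are denser ("Sleep diary data will also be acquired continuously throughout the 8 study-weeks in both groups"), so richer random effects can be fitted there. The scenarios in step 5 show what could happen on one reading. They are not evidence that this trial's tests are wrong in a given direction or by a given amount.

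**What to change.** 1. **Hypothesis 3.** Keep the baseline to 6-month contrast. Add the post-treatment to 6-month change in the CBTi group, with its 95% CI, as the analysis for Hypothesis 3 and Aim 3.
2. **Criterion.** State in advance how much of the gain must be retained, and judge the estimate and CI against that. State that a non-significant difference will not be taken as maintenance. At change SD 1.0, an allowed loss smaller than about 0.32 to 0.39 SD could not be confirmed even if the observed loss were zero.
3. **Model for the contrasts.** Say whether baseline is a covariate or a response. If it is a covariate in the treatment-effect model, describe the separate model, with baseline, post-treatment and 6-month scores as responses, that yields the 6-month contrasts.
4. **Covariance for the questionnaire outcomes.** State it, preferably unstructured by visit with a small-sample df method. If a simpler structure is the fallback, pair it with robust SEs. State the random terms for diary outcomes separately.

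**Cost.** Items 1 to 3 are SAP wording and use data already scheduled. Item 4 may need a different R fitting function from the one named. An unstructured matrix over four visits has 4 variances + 6 covariances = 10 parameters, with 6-month data from one arm only, so there is some convergence risk. The df method matters: in simulated trials with dropout that used simple fixed df, the post-treatment to 6-month test ran at 6.9% to 7.7% against a nominal 5%. The main remaining limitation is the wide interval, which may leave the maintenance question open.
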